### **13.2. Vital Signs**

Vital signs will be measured by a qualified staff member at Visit 1, Visit 9 and Visit 13. The following items will be measured:

- Body temperature;
- Heart rate;
- Respiration rate;
- Blood pressure (systolic and diastolic) after the subject sits quietly for at least 5 minutes;
- Height (at Visit 1 only);
- Weight (at Visit 1 only);

Any measure that is, in the opinion of the investigator, abnormal AND clinically significant (CS must be recorded as history if found prior to the first study medication treatment or as an AE if found after the first study medication treatment begins.

### **13.3. Clinical Laboratory Sampling**

Non-fasting blood samples for clinical laboratory analysis will be collected by a qualified staff member at Visit 1 and Visit 13. Approximately 7.5 mL of blood will be collected for each chemistry sample and 3 ml of blood will be collected for each complete blood count (CBC). These blood samples will be sent to a central laboratory for analysis. Refer to the study specific laboratory manual for instructions regarding handling of the blood samples and shipping instructions.

The following tests, at a minimum, will be conducted:

#### **Chemistry Panel**

Albumin

#### **Complete Blood Count**

Hematocrit

|                                  |                               |
|----------------------------------|-------------------------------|
| Alkaline phosphatase             | Hemoglobin                    |
| Alanine aminotransferase (ALT)   | Platelet count                |
| Aspartate aminotransferase (AST) | Red blood cell morphology     |
| Blood urea nitrogen (BUN)        | Red blood cell count          |
| Bicarbonate                      | White blood cell count        |
| Calcium                          | White blood cell differential |
| Chloride                         | % & absolute                  |
| Creatinine                       | Basophils                     |
| Glucose                          | Eosinophils                   |
| Lactate dehydrogenase (LDH)      | Lymphocytes                   |
| Phosphorus                       | Monocytes                     |
| Potassium                        | Neutrophils                   |
| Sodium                           |                               |
| Total bilirubin                  |                               |
| Total protein                    |                               |
| Uric acid                        |                               |

The results of the clinical laboratory tests will be reported on the central laboratory's standard reports. These laboratory results will be sent to the investigator via fax. The investigator must review all laboratory reports in a timely manner and note NCS or CS to define the clinical relevance of any result that is outside the normal range for the laboratory. The investigator must date and initial every laboratory report.

The investigator must review the Visit 1 laboratory results for all the measured analytes for each subject prior to Visit 2. The subject must not be randomized at Visit 2 if any of the Visit 1 results are outside normal range for the laboratory AND, in the opinion of the investigator, CS.

The investigator must report all laboratory results that are BOTH outside the normal range for the laboratory AND, in the opinion of the investigator, CS as medical history if found prior to the first study medication treatment or as an AE if found after the first study medication treatment begins.

### **13.4. Demographics and Medical History**

At Visit 1, the investigator or designee will collect demographic information including date of birth, sex at birth, race and, if appropriate, ethnicity for each subject.

At Visit 1, the investigator must determine each subject's Fitzpatrick skin type and document appropriately on the subject's CRF.

**Table 4: Fitzpatrick Skin Type Scoring System**

| Skin Type Classification | Description   |
|---------------------------------|--|
| Type I                          | always burns, never tans (pale white; blond or red hair; blue eyes; freckles)              |
| Type II                         | usually burns, tans minimally (white; fair; blond or red hair; blue, green, or hazel eyes) |
| Type III                        | sometimes mild burn, tans uniformly (cream white; fair with any hair or eye color)         |
| Type IV                         | burns minimally, always tans well (moderate brown)   |
| Type V                          | very rarely burns, tans very easily (dark brown)   |
| Type VI                         | Never burns, never tans (deeply pigmented dark brown to darkest brown)                     |

(Fitzpatrick, TB, 1988)

Medical history information will be recorded including all medical conditions and disease states that, at Visit 1:

- Are ongoing
- Require concomitant therapy

Are, in the opinion of the investigator, relevant to the subject's study participation.

## **14. ADVERSE EVENTS**

### **14.1. Definitions**

#### **14.1.1. Adverse Events (AEs)**

An adverse event (AE) is any untoward medical occurrence in a patient that develops or worsens in severity during the conduct of a clinical study of a pharmaceutical product and does not necessarily have a causal relationship to the study drug. An adverse event can, therefore, be any unfavorable and unintended physical sign, symptom, or laboratory parameter that develops or worsens in severity during the course of the study, or significant worsening of the disease under study (or any concurrent disease), whether or not considered related to the study drug.

Accordingly, an adverse event could include any of the following:

- intercurrent illnesses;
- physical injuries;
- events possibly related to concomitant medication;
- significant worsening (change in nature, severity, or frequency) of the disease under study or other pre-existing conditions. (NOTE: A condition, recorded as pre-existing, that is intermittently symptomatic [e.g., headache] and which occurs during the study should be recorded as an adverse event);
- Drug interactions;
- Events occurring during diagnostic procedures or any washout phase of the study;
- laboratory or diagnostic test abnormalities occurring after the start of the study (i.e., after screening and once confirmed by repeat testing) that results in the withdrawal of the patient from the study, requires medical treatment or further diagnostic work-up, or is considered by the study investigator to be clinically significant. NOTE: Abnormal laboratory test results at the screening visit that preclude a patient from entering the study or receiving study treatment are not considered adverse events, but will be recorded to monitor data from patients who do not meet screening criteria.

**Worsening of any of the identified common wart assessments should be reported as an AE ONLY if the use of the study medication is interrupted or discontinued or if therapy is required to manage the event.**

**The investigator must, for any common wart related AE, question the subject in detail to determine if there are any confounding factors (e.g., irritation by clothing or activity, sunburn) for any such AE.**

The investigator should, when certain, report a diagnosis rather than the signs, symptoms or clinically relevant abnormal laboratory values associated with the AE. Otherwise, signs, symptoms or abnormal laboratory values may be used to describe the AE.

Any CS abnormality discovered prior to the first study medication treatment should be reported as medical history, not as an AE.

#### **14.1.2. Serious Adverse Events (SAEs)**

A Serious Adverse Event is any untoward medical occurrence that at any dose:

- Results in death;
- Is life threatening;
- Requires inpatient hospitalization or prolongation of existing hospitalization;
- Results in persistent or significant disability/incapacity,
- Is a congenital anomaly/birth defect or
- Is an important medical event.

The term “life threatening” refers to an event in which the subject was at risk of death at the time of event; it does not refer to an event that hypothetically might have caused death if it was more severe.

Inpatient hospitalization is considered to have occurred if the subject is admitted to the hospital on an in-patient basis, even if released the same day. Prolongation of hospitalization is defined as an additional night stay in the hospital. Hospitalization for elective treatment of a pre-existing condition that did not worsen from baseline is not considered an AE.

Important medical events are those that may not be immediately life threatening, result in death or hospitalization, but are clearly of major clinical significance and may jeopardize the subject or require intervention to prevent one of the outcomes listed in the SAE definition above. These should also usually be considered serious. Examples of such events are intensive treatment in an emergency room or at home for allergic bronchospasm, blood dyscrasias or convulsions that do not result in hospitalization.

#### **14.1.3. Adverse Event Reporting Period**

The investigator must start reporting non-serious AEs starting with the subject’s first study medication treatment continuing until Visit 11. Non-serious adverse events that occur between the time the subject was consented and the first application of study medication will be reported as medical history.

Reporting for SAEs begins after the subject signs the informed consent and continues until Visit 11 (regardless of relationship to study medication). If a subject experiences a SAE after Visit 11 that is deemed by the investigator to be related to study medication, the investigator must report this to the Sponsor using the study specific SAE report form.

#### **14.1.4. Severity**

The investigator must define the severity of each AE using the following definitions as a guideline. The investigator will consider the range of the possible severity of the event and identify the severity that is the most appropriate according to her/his medical judgment.

**Mild** – Awareness of signs or symptom, but easily tolerated

**Moderate** – Discomfort, enough to cause interference with usual activity

**Severe** – Incapacitating with inability to perform usual activity.

#### **14.1.5. Relationship to Study Medication**

The investigator will determine if there is a reasonable causal relationship between the study medication and an AE or not. The investigator will use her/his best medical judgment and consider all relevant factors (e.g., temporal relationship, location of the event, the subject's relevant medical history, concomitant therapies and concurrent conditions) to determine the relationship of the AE to the study medication. The investigator will define the relationship of an AE to the study medication by selecting one of the following categories.

**Related** – There is a reasonable possibility that there is a causal relationship between the study medication and the AE.

**Not Related** – There is not a reasonable possibility that there is a causal relationship between the study medication and the AE.

The term “reasonable causal relationship” means there are facts or arguments to suggest a causal relationship (International Conference on Harmonization (ICH) E2A).

### **14.2. Reporting Procedures**

#### **14.2.1. Procedures for Reporting Adverse Events**

At each post enrollment visit, the investigator or designee will question the subject to elicit AEs using a non-directive question such as “Has there been any change in your health since the previous study visit?”

The Investigator/designee will monitor the subject for at least 20 minutes after the Treatment Completion Time at any visit during which a study medication treatment is performed to elicit AEs in a similar manner.

If appropriate, based on the subject's response to non-directed questioning regarding AEs, the investigator or designee will follow-up with directed questions and appropriate evaluations.

Any AE noted during the reporting period must be reported in the source documents and on the appropriate AE CRF.

AEs that are defined as “Not Related” to the study medications will be followed until they are resolved or until the subject's last study visit. AEs that are defined as “Related” to the study medications will be followed until they are resolved or, if not resolved after the subject's last study visit, until in the opinion of the investigator, the AE reaches a clinically stable outcome with or without sequelae.

#### **14.2.2. Procedure for Reporting Serious Adverse Events**

Upon becoming aware of a SAE occurring during the AE reporting period, whether or not related to the study medications, the investigator must:

1. Take the appropriate medical action to ensure the subject's safety

Aclaris Therapeutics, Inc.

Protocol Number: A-101-WART-302

Amendment 3: Version 5 14 February 2019

2. Immediately inform Aclaris of the SAE:

**Serious Adverse Event [contact]**

3. Within 24-hours of becoming aware of the event, a SAE report form, an AE CRF and any other relevant information (e.g., concomitant medication CRF, medical history CRF, laboratory test results) must be faxed to the SAE Fax line listed above.
4. Monitor and document the progress of the SAE until it resolves or, if not resolved after the subject's last study visit, until in the opinion of the investigator the AE reaches a clinically stable outcome with or without sequelae AND the investigator and Drug Safety Monitor agree that the SAE is satisfactorily resolved.
5. Inform the Drug Safety Monitor of SAE updates by telephone followed by an SAE form update sent by fax or by e-mail.

Comply with the appropriate regulatory requirements and Aclaris Therapeutics, Inc. instructions regarding reporting of the SAE to the responsible Institutional Review Board (IRB) or Ethics Committee (EC).

#### **14.2.3. Withdrawal Due to an Adverse Event**

Any patient who experiences an adverse event may be withdrawn from study drug at any time at the discretion of the investigator. If a patient is withdrawn wholly or in part because of an adverse event, both the adverse events page and termination page of the CRF will be completed at that time. The patient will be monitored until the event has resolved or stabilized, until a determination of a cause unrelated to the study drug or study procedure is made, or until the patient is referred to the care of a local health care professional. The investigator must inform the medical monitor as soon as possible of all patients who are being considered for withdrawal due to adverse events. Additional reports must be provided when requested.

## **15. STATISTICAL CONSIDERATIONS**

### **15.1. Sample Size and Power Considerations**

Based on efficacy results from study A-101-WART-203 with the same active study medication and treatment plan specified in the current protocol for a comparable patient population and indication, an overall per-wart clearance rate of at least 26% for Active compared with 9% for Vehicle is anticipated. Assuming a distribution of treated warts per subject comparable to the Phase 2 study results, statistical modeling provided a forecast of an advantage in subject responder rates (all treated warts with PWA=0) for Active over Vehicle groups of at least 11 percentage points. This leads to a required sample size for the current study of approximately 500 subjects to provide greater than 90% power to achieve statistical significance in the primary efficacy analysis. This projection takes into account the impact of the anticipated subject dropout rate on power for the primary efficacy analysis, based on the Intent-to-Treat (ITT) population and planned missing data imputation procedures.

Additionally, a simulation was conducted in a manner that accounted for the distribution of multiple warts, the treatment effect in clearance between the different warts and the correlation in wart clearance among multiple warts. Specific details of the simulation are described in the SAP. Results of this simulation indicate that data from 500 subjects (250 per group) will provide 97% power to demonstrate the superiority of 45% A-101 topical solution over vehicle for the primary endpoint.

### **15.2. Analysis of Populations**

The populations used for analyses will be defined as follows:

- Intent-to-Treat Population (ITT): The ITT population includes all randomized subjects.
- Per-Protocol Population (PP): The PP Population includes all subjects who received at least one application of study medication and have no major protocol violations.
- Safety Population: The Safety population includes all subjects who received at least one application of study medication.

### **15.3. Statistical Analysis of Efficacy**

The ITT population will be used for primary and secondary efficacy analyses and summaries. The ITT population is defined as all subjects randomized to the study and analyzed as randomized. The Per-Protocol (PP) population will be used for sensitivity analyses for the primary efficacy analysis and all secondary efficacy analyses included in the hierarchical testing procedure. Details on all analyses discussed below will be provided in the study Statistical Analysis Plan (SAP).

The primary efficacy analysis will be a treatment comparison of A-101 45% compared to Vehicle at Visit 10 (Day 60). It will be based on the proportion of subjects who achieve complete clearance (PWA=0) of all identified common warts. A Cochran Mantel Haenszel (CMH) test stratified by the baseline number of treated warts will be used to perform the primary

efficacy comparison between treatment groups, with 2-tail alpha set at 0.05. The analysis will be based on the ITT population. Any identified common wart for a randomized subject that has missing data at the endpoint visit will be treated as not Clear for the purpose of the primary efficacy analysis.

The first sensitivity analysis for the primary endpoint will be an analysis based upon the PP population. This analysis will use the same CMH model described for the primary analysis. A second sensitivity analysis will be conducted for the primary endpoint using the same CMH model for the ITT population that includes the imputation of missing PWA data using a fully conditionally specified (FCS) regression-based Multiple Imputation (MI) procedure. To assess the impact of missing data imputation on the primary analysis results a tipping point analysis will be conducted. This analysis will shift the treatment coefficient in the regression model used in the MI procedure to impose a worse mean maximum PWA for the A-101 45% arm and a better mean maximum PWA for the vehicle arm. Details of this tipping point analysis will be specified in the SAP. In addition, a model similar to the primary analysis model but stratified instead by Study Center will be performed as a sensitivity analysis including a Breslow-Day test to evaluate heterogeneity across sites.

Four secondary efficacy analyses will be performed and tested in a hierarchical Fixed-Sequence step-down method to control alpha among secondary efficacy variables. The predefined order of the tests is specified to be the order of these analyses as presented below. All analyses will be conducted at the same alpha level (2-tail alpha = 0.05). The results of the second analysis will only be reported if the first analysis reaches statistical significance at alpha = 0.05. The results of the third analysis will only be reported if the first and second analyses reach statistical significance, each at alpha = 0.05. The results of the fourth analysis will only be reported if the first, second and third analyses reach statistical significance, each at alpha = 0.05. Each of the analyses will focus on the outcome of identified common warts at specified time points.

The first secondary analysis will evaluate the effectiveness of A-101 45% compared to Vehicle at Visit 13 (Day 137). It will be based on the proportion of subjects who achieve complete clearance (PWA=0) of all identified common warts. A Cochran Mantel Haenszel (CMH) test identical to the primary efficacy analysis model and stratified by the number of treated warts at baseline will be used to perform the comparison between treatment groups, with 2-tail alpha set at 0.05. Any randomized subject with missing data at the Day 137 visit will be treated as not Clear for the purpose of this secondary efficacy analysis. Sensitivity analyses specified for the primary efficacy analysis will also be performed for this efficacy time point, including missing data imputation impact analyses, the tipping point analysis, and the site heterogeneity analysis.

The second secondary efficacy analysis will be based on a comparison between A-101 45% and Vehicle of the mean per-subject percent of treated warts that are Clear (PWA=0) at Visit 13 (Day 137), using an analysis of variance (ANOVA) model with 2-tail alpha set at 0.05.

The third secondary efficacy analysis will be a comparison between A-101 45% and Vehicle of the proportion of subjects with a single wart at baseline, whose wart is Clear (PWA=0) at Visit 10, using a CMH test stratified by investigator site, with 2-tail alpha set at 0.05.

The fourth secondary efficacy analysis will a comparison between A-101 45% and Vehicle s with respect to the median time to achieve onset of Clearance (PWA=0) for all treated warts. It will be conducted as a comparison of median time for a subject to first achieve Clearance (PWA=0) of all treated warts, using a log rank test with 2-tail alpha set at 0.05. This will be a Kaplan-Meier time-to-event analysis providing standard survivor functions and comparisons of time-to-event curves using the log rank test, where time-to-event curves will be compared with two-tail alpha = 0.05, and median time to event will be presented for each treatment group. For each subject the time to achieve onset of complete treated wart Clearance will be calculated from the date of randomization to the earliest visit date when all treated warts are clear. In the event a subject does not attain complete wart Clearance, that subject's time-to-event data will be treated as censored for the Kaplan-Meier analysis.

#### **15.4. Statistical Analysis of Safety Data**

Descriptive statistics will be calculated on the safety parameters using the Safety Population and using actual treatment received. The proportion of subjects with treatment-emergent adverse events will be tabulated and presented by treatment and Medical Dictionary for Regulatory Activities (MedDRA) System Organ Class. Vital signs, LSR scores and clinically relevant abnormal laboratory results will also be tabulated and presented by study medication. No inferential testing will be performed.

Safety summaries by study medication group will include listings by study medication of adverse events incidences within each MedDRA System Organ Class, and changes from pre-application values in vital signs. Adverse event summaries will be presented by study medication showing the proportion of subjects experiencing adverse events, both overall and by MedDRA System Organ Class. The version of MedDRA to be used for the analysis of this study will be specified in the Statistical Analysis Plan.

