#### 3.3.2 Adverse Events

Adverse events are coded using the MedDRA (Version 22) dictionary and are categorized by system organ class (SOC) and preferred term (PT). Only treatment emergent adverse events are included in summary tabulations (i.e. adverse events occurring on or after the first application of study medication and within 30 days following the last application of study medication). All adverse events are included in the data listings including those that are not considered treatment emergent.

To allow differentiation as to which study period an Adverse Event occurred, three categories are defined based upon onset date. Adverse Events that had onset dates prior to the first application of study medication are considered "prior". Adverse events with onset dates on or after the first application of double-blind study medication and within 30 days following the last application of study medication are considered "treatment emergent". Events with onset dates more than 30 days after the last application of study medication are considered as "post-therapy".

Frequency tabulations are presented by MedDRA SOC and preferred term, for all adverse events; study treatment-related, adverse events resulting in discontinuation of study treatment, serious adverse events and adverse events by maximum severity. Adverse events resulting in discontinuation are those with 'action taken' recorded as 'drug withdrawn'.

Treatment emergent adverse event summaries by MedDRA SOC and preferred term will also be provided according to the following subgroups:

- Age (<18, 18 to 65, and >65)
- Sex (Male, Female)
- Race (White, Non-White)

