### **3.3.5 Laboratory Evaluations**

Shift tables showing changes in relationship to the normal reference range grade from baseline to the "worst" relationship recorded post-baseline are tabulated. In the event a subject had both "low" and "high" post-baseline values the subject will be counted under both "low" and "high". As such, the percentages of the cells in the shift table may add to more than 100%.

Chemistry and hematology parameters are summarized using descriptive statistics for

each visit. Both actual values and changes from baseline will be summarized.

The number and percentage of subjects meeting criteria for hepatobiliary abnormalities will be provided.

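### Protocol 15.4 commits to tabulating clinically relevant abnormal laboratory results by arm, but no SAP summary table identifies a Visit 13 result as clinically significant, and the adverse event tables do not fill the gap

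*Protocol*

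**What the plan says.** **The commitment.** Protocol Section 15.4, on safety analysis: "Vital signs, LSR scores and clinically relevant abnormal laboratory results will also be tabulated and presented by study medication".

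**What makes a result clinically relevant.** Protocol Section 13.3 has the investigator review each laboratory report and "note NCS or CS to define the clinical relevance of any result that is outside the normal range for the laboratory". The same section continues: "The investigator must report all laboratory results that are BOTH outside the normal range for the laboratory AND, in the opinion of the investigator, CS". Such a result goes into medical history if found before treatment, or is reported "as an AE if found after the first study medication treatment begins".

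**When blood is drawn.** Protocol Section 13.3 says that samples "will be collected by a qualified staff member at Visit 1 and Visit 13". Visit 13 is therefore the only scheduled post-baseline sample.

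**What the SAP plans.** SAP Section 3.3.5 has three outputs:
- "Shift tables showing changes in relationship to the normal reference range grade from baseline" to the worst post-baseline category;
- descriptive statistics by visit, where "Both actual values and changes from baseline will be summarized";
- a number and percentage of subjects meeting hepatobiliary criteria, which that section does not define.

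**How AEs are summarised.** SAP Section 3.3.2: "Only treatment emergent adverse events are included in summary tabulations". The treatment-emergent period runs from the first application to 30 days after the last. Events with later onset are classed as post-therapy and appear in listings only.

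**When AE reporting stops.** Protocol Table 2 (footnote 17) and Section 14.1.3 end AE reporting at Visit 11. The exceptions are AEs related to local skin reactions (footnote 17) and later serious events judged related to study medication (14.1.3).

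**The concern.** Safety is a stated secondary objective, and the protocol asks investigators to separate laboratory abnormalities that matter from those that do not. Section 15.4 promises the reader that separation by arm. The SAP instead summarises every excursion from the normal range on the same footing, so the clinical judgement is lost at the summary stage. One would expect the AE tables to recover it, because a CS result after the start of treatment is meant to become an AE. The sampling schedule prevents that for the one scheduled post-baseline sample.

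At stake is whether a reader of the safety tables can compare the arms on abnormalities that an investigator considered important, outside whatever liver criteria are applied.

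**Working it through.** The plan gives no figure to reproduce here. The check is a comparison of sections followed by day arithmetic.

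**1. Does any laboratory table use the CS mark?**

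| SAP 3.3.5 output | Is a numeric CS result counted? | Is it identified as CS? |
|---|---|---|
| Shift table, low/normal/high | Yes; a reportable CS result is out of range by definition | No |
| Descriptive statistics by visit | Yes, as a value and a change | No |
| Hepatobiliary count | Only if it meets those criteria | No |

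Red cell morphology, which is not numeric, may not fit the first two tables; the SAP does not say.

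**2. Can the AE tables show it?**

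Inputs:
- last scheduled application: Day 53, at home (Protocol Section 7), with a window of +1 day (Table 2), so Day 54 at the latest;
- treatment-emergent window: 30 days after the last application (SAP 3.3.2);
- Visit 13: Day 137 with a window of +7 days (Table 2), so Day 137 to 144.

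Window closes = last application day + 30:
- 53 + 30 = Day 83;
- 54 + 30 = Day 84.

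Visit 13 minus last application:
- from Day 53: 137 − 53 = 84 to 144 − 53 = 91 days;
- from Day 54: 137 − 54 = 83 to 144 − 54 = 90 days.

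Shortest distance past the window: 137 − 84 = 53 days. Longest on this schedule: 144 − 83 = 61 days. A subject who stops treatment early but still attends Visit 13 is further out. An abnormality first found at Visit 13, with onset dated then, is always post-therapy.

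**3. Is it certain to be collected as an AE?**

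No. Protocol 13.3 sets no end date for reporting a CS result as an AE, whereas Table 2 footnote 17 and Section 14.1.3 stop at Visit 11 (Day 78). A non-serious laboratory AE with no local skin reaction meets neither exception. Even the listing is not assured.

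**4. Can the shift table stand in for a CS table?**

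For illustration, assume that 2% to 5% of values per analyte fall out of range by chance; this rate is not in the documents. With 250 subjects per arm that gives 250 × 0.02 = 5 to 250 × 0.05 = 12.5 values per analyte per arm. A CS result would sit unmarked among them. The conclusion does not depend on this rate.

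**The case against.** **The result is still in a table.** A reader might infer that a CS result at Visit 13 appears in no summary table. The documents do not support that. A CS result must be out of range, so a numeric one enters the shift table and the descriptive statistics, and a liver result may enter the hepatobiliary count. What is lost is the identification. The shift table also cross-classifies by baseline, so a sizeable imbalance in one analyte could still show.

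**An undeclared change.** A reader might infer that SAP Section 3.6 should have declared this as a departure from the protocol. That cannot be established. The SAP Introduction says it was written for protocol Version 4; Section 15 was updated in Version 5, and the Version 4 laboratory wording is not available. SAP 3.6 describes the Safety Population as new relative to the protocol, although the current Section 15.4 already uses it. Only a mismatch between the current documents can be shown.

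**Noise hides everything.** With 27 numeric analytes and the assumed 2% to 5% rate, 1 − 0.98^27 = 42% to 1 − 0.95^27 = 75% of subjects would have at least one out-of-range value, if analytes were independent. That is tempting as a measure of the problem, but it rests on assumed rates and describes no planned table.

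**Clinical relevance is not defined as CS in Section 15.4.** True; the link comes from Section 13.3. It is the only operational definition the protocol offers, so the reading is reasonable.

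**Other samples may exist.** Protocol Section 8.4 foresees withdrawal for a clinically significant laboratory result, and SAP Appendix B allows for unscheduled and early termination visits. A sample within 30 days of the last application could yield a treatment-emergent AE. This stands, but it does not cover the scheduled sample.

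**Limited information.** A sample 83 to 91 days after the last scheduled application says little about effects during treatment, and no inferential safety testing is planned. This limits the consequence and does not remove the commitment.

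**Conclusion.** The point holds in a limited form. The current protocol commits to a by-arm tabulation that none of the three SAP laboratory outputs provides. The AE tables cannot supply it for the scheduled post-baseline sample, which falls at least 53 days after the treatment-emergent window has closed.

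This rests on reading clinical relevance as the CS mark of Section 13.3, and on an abnormality first found at Visit 13 being given an onset date at that visit. The number of CS results to be expected cannot be estimated from the documents, so no size can be put on a missed imbalance. The issue is one of completeness and clarity in safety reporting; it does not affect the efficacy analysis. It is worth correcting because the protocol already promises the output.

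**What to change.** **Add to SAP Section 3.3.5:** the number and percent of subjects per arm (Safety Population, actual treatment received) with at least one post-baseline result that is out of range and judged CS, overall and by analyte, at any time after the first application. Keep the three existing outputs.

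**Reconcile the collection rules:** Protocol 13.3 (a CS result found after first treatment is reported as an AE), Protocol Table 2 footnote 17 and Section 14.1.3 (AE reporting ends at Visit 11) and SAP 3.3.2 (treatment-emergent window). The documents should say how a CS result at Visit 13 is recorded, so that the data feeding the table exist.

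**Cost:** one extra table and SAP wording. There may also be data capture. Section 13.3 has the investigator note CS or NCS on laboratory reports that are dated and initialled, and nothing says that the mark reaches the database. If it exists only on those reports, it must be entered, or taken from the AE case report form where the result was reported there. SAP 3.6 records a correction made after unblinding, so a late addition should be documented as carrying out the commitment in Protocol 15.4.
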